If a medical adverse event should occur, study staff includes two physicians who are board-certified in psychiatry (Drs. [name] and [name]). Additional medical assistance will be available through the VA TMS clinical roll-out staff RN's and physicians trained in TMS safety and adverse event management, and VA Palo Alto HCS Emergency Department service is readily available, if needed. Immediate psychiatric/psychological consultation will available for participants if required ([name]: Licensed Clinical Psychologist and [name]: Board Certified Psychiatrist). Appropriate referrals will be made when necessary in the judgment of the PI/PD or study physician.

g) Lead Investigator or Coordinating Institution in Multi-site Study.

Please explain (i) your role in coordinating the studies, (ii) procedures for routine communication with other sites, (iii) documentation of routine communications with other sites, (iv) planned management of communication of adverse outcomes, unexpected problems involving risk to participants or others, protocol modifications or interim findings.

1. Purpose

a) In layperson's language state the purpose of the study in 3-5 sentences.

The purpose of this study is to evaluate the efficacy of intermittent theta burst (iTBS) transcranial magnetic stimulation (TMS) as a treatment for Veterans with an alcohol use disorder (AUD) to decrease the exceedingly high rate of relapse associated with this condition.

b) State what the Investigator(s) hope to learn from the study. Include an assessment of the importance of this new knowledge.

At least 60% of those with AUD will experience a major relapse period within 6 months of treatment, irrespective of the intervention

(psychosocial and/or pharmacological) employed. Consequently, the high prevalence of AUD and relapse following treatment in Veterans is associated with substantial resource allocation and costs for the DVA Health Care System. Current pharmacological and psychosocial interventions demonstrate only a moderate level of efficacy, which is reflected in the high rate of relapse in AUD.

iTBS-TMS is a neurostimulation method that is at the forefront of innovative, non-invasive, and safe treatments for AUD, and the disorders that commonly co-occur with AUD. To reduce the high rate of relapse in Veterans with AUD, it is necessary for interventions to more effectively address the associated neurobiological dysfunction and salient co-occurring conditions.

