Design, Treatment Phase and Treatment Arms: This is a double-blind randomized group design, which will enroll 40 participants. After screening and baseline procedures, participants will be randomized to active or sham iTBS-TMS conditions (20 active, 20 sham); thus participants will have a 50% probability of receiving active treatment. Participants will receive 20 iTBS-TMS sessions over the course of 2 weeks. Participants will be required to be abstinent from alcohol and illicit substance for 7 days and demonstrate no clinically significant withdrawal symptoms prior to randomization.

Rationale for Brain Region Site: The left dorsolateral prefrontal cortex (DLPFC) was chosen as the iTBS stimulation site given excitatory transcranial magnetic stimulation to this region has been demonstrated to decrease cravings in non-Veterans with AUD. Additional stimulation of this site has been robustly shown to be associated with decreased unipolar depressive symptomatology; depressive disorders are highly comorbid in Veterans with AUD.

Duration of Treatment Phase: Active iTBS-TMS Treatment Group – will receive a total of 20 treatments delivered 5 days/week, two treatments per day (Monday-Friday), over 2 consecutive weeks. Sham Treatment group will receive the same frequency and

duration of treatment, without actual administration of iTBS-TMS. iTBS-TMS sessions will be delivered prior to the beginning of participants' treatment day, and at lunch, as to not interfere with their treatment-as-usual in the VA substance treatment clinics. There have been no adverse events reported in the literature implementing two iTBS sessions per day in any population.

Procedures for Delivery of iTBS-TMS Sessions:

1) Anatomical localization of the left DLPFC for the stimulation coil will be individualized for each participant and achieved through standardized procedures for EEG electrode placement, optimized for transcranial magnetic stimulation. The localization of participant left DLPFC will be confirmed using the subject MRI data collected prior to the treatment phase.

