Post-Treatment Phase: Within 3-4 days of completion of the Treatment Phase, all participants will repeat neurocognitive assessment, select psychiatric assessment measures, select alcohol and substance questionnaires, 3 Tesla Magnetic Resonance Neuroimaging and blood draw as described above in Baseline/Pretreatment Assessment. Monthly Follow-ups: For the 6 months following completion of the treatment phase, participants will be contacted monthly, via telephone or in person, to complete a brief standardized measures of alcohol and substance use, as well as craving to assess for changes in these variables over the preceding 30 days. These brief contacts will be 15-20 min in duration and tracking sobriety is the primary outcome measure of this study.

b) Explain how the above research procedures are the least risky that can be performed consistent with sound research design.

All procedures will be performed by staff trained specifically for the tasks for which they are responsible. All procedures, including the iTBS-TMS, are considered low-risk procedures. iTBS-TMS is regarded as safe and without lasting side effects when established

guidelines are followed. The primary serious adverse event associated with transcranial magnetic stimulation procedures are seizures,

however, the estimated prevalence is very low at < 1%. In the case of transcranial magnetic stimulation-seizures, all have occurred during stimulation, there was no recurrence of seizures, and no incidences of status epilepticus. There have been no significant adverse cognitive, brain structural, neurologic or cardiovascular sequelae reported as a result of iTBS-TMS. Seizure risk will be minimized by careful patient selection (by rigorously screening and exclusion of participants with history

of seizure disorders or other conditions and medication use that increases risks of seizure). A seizure protocol is in place to avoid participant injury in the event that a seizure does occur (attached). Overall, the risks to participants in this proposal are reasonable in relation to anticipated benefits, if any, to the participants, and the importance of the knowledge that may be expected to result.

c) State if deception will be used. If so, provide the rationale and describe debriefing procedures. Since you will not be fully informing the participant in your consent process and form, complete an alteration of consent (in section 13). Submit a debriefing script (in section 16).

N/A

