a) For the following categories include a scientific estimate of the frequency, severity, and reversibility of potential risks. Wherever possible, include statistical incidence of complications and the mortality rate of proposed procedures. Where there has been insufficient time to accumulate significant data on risk, a statement to this effect should be included. (In describing these risks in the consent form to the participant it is helpful to use comparisons which are meaningful to persons unfamiliar with medical terminology.)

Investigational devices.

iTBS-TMS device: iTBS-TMS is regarded as safe and without lasting side effects when established guidelines are followed. The primary safety concern associated with any form of transcranial magnetic stimulation procedures are seizures, however, the estimated prevalence is very low at < 1%. In the case of transcranial magnetic stimulation-seizures, all have occurred during stimulation, there was no recurrence of seizures, and no incidences of status epilepticus. All the reported seizures resolved promptly after removal of stimulation, without medical intervention and were not associated with lasting adverse effects. In those rare seizure cases, the motor cortex was typically being stimulated; in the proposed study a non-primary motor region of the cortex (left DLPFC) is the stimulation site. There have been no significant adverse cognitive, brain structural, neurologic or cardiovascular sequelae reported as a result of iTBS-TMS.

Participants treated with iTBS-TMS may experience temporary discomfort at the site of stimulation due to depolarization of sensory and motor neurons in the scalp under the point of stimulation. Muscle tension headache may result in some participants (generally estimated at less than 10% of sessions), and can persist for 1-2 hours post stimulation. iTBS treatment can result in mild to moderate headaches in approximately 15% of participants. These headaches are never disabling or persistent and usually respond to ibuprofen or acetaminophen. The incidence of headaches in those with serial transcranial magnetic stimulation typically diminishes with increasing number of sessions. In some people, particularly those with a history of a history of Bipolar Disorder I or II, daily transcranial magnetic stimulation caused them to experience mania (increased energy, no need for sleep, and racing thoughts); this study will exclude for a history of Bipolar Disorders.

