Neurocognitive and psychiatric interview sessions will include breaks. In the event that a study participant appears to be under undue strain, the test or interview session will be discontinued. Participants will be reminded that they are free to withdraw from participation at any time.

iTBS-TMS administration: The iTBS-TMS operator will be the PI ([name]) and he is fully trained and qualified to administer the procedure according to current safety practices and standards of care in research and clinical settings. Co-Investigators trained in iTBS-TMS will closely monitor the iTBS-TMS PIs adherence to safety protocols and administration for this proposal. This application employs all current established and standard iTBS-TMS treatment safety and monitoring for adverse events guidelines. The iTBS-TMS operator will monitor all participants for ear protection, coil placement, and seizure activity during all sessions. All participants will be required to have abstained from alcohol or non-prescribed medication for 7 consecutive days prior to the first rTMS session. Prior to the first rTMS session, participants will be administered the Clinical Institute Withdrawal Assessment for Alcohol-Revised and must score ≤ 8 (scores > 8 are indicative of potential autonomic instability); participants with a score > 8 will immediately be escorted to their VA Palo Alto Addiction Treatment Services clinic for further evaluation. Participants will be randomly screened x6 for alcohol (breath alcohol) and substance use (urine toxicology) prior to rTMS sessions during the 2 week treatment phase. If a participant tests positive or report any alcohol or substance use during the 2 week iTBS-TMS treatment period, they will be immediately withdrawn from the study. Additionally, prior to each session, participants will complete a iTBS-TMS screen, which will include inquiring about any changes in medications or comorbid medical conditions, amount of sleep, suicide screening questionnaire prior to each rTMS session to assess for current suicide risk. Although patients in the study are regularly screened for alcohol and substance use and suicide risk while in treatment, we will conduct random alcohol/substance screening and pre-iTBS-TMS session suicide risk assessment to ensure participant welfare. Should a headache or site discomfort occur, these symptoms usually readily respond to acetaminophen or ibuprofen. Any reported painfulness typically improves over time or completely remits. To protect against possible hearing damage, participants will wear ear protection during rTMS sessions (foam ear plugs and noise attenuating headphones). This will greatly reduce the possibility of hearing loss. Hearing acuity testing pre-and-post rTMS is no longer a standard practice, given the remote likelihood of iTBS-TMS-related hearing loss.

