
Additional Procedures for the Monitoring of Seizures and Suicidal Ideation/Behavior:

Screening, Baseline and Treatment Phase: In the unlikely event that a seizure does occur, participants will be closely monitored and treated for any medical or psychological consequences. rTMS sessions will be conducted at the VA Palo Alto MIRECC, which fully equipped to safely handle a seizure. If at any point during study participation, a participant has a seizure, the participant will be withdrawn from the study immediately (although they will still be followed for protocol assessments). All seizures will be considered serious adverse events (SAE) and as such, will be reported to the study PI. We will immediately suspend enrollment if 10 participants experience a seizure during study participation, and request that the Data Monitoring Committee (DMC) evaluate the SAE data, to determine if enrollment of new participants should be resumed without protocol changes, if protocol modifications should be made before resuming enrollment, or if the study should be terminated. We recognize that study termination or modification based on SAEs, such as seizures, ultimately rests with the DMC and the study PI.

If a participant expresses suicidal ideation/intent, and is determined to be a risk to self, a clinical evaluation will be immediately conducted by the PI (a licensed clinical psychologist), Co-Is (a licensed clinical psychologist or board certified psychiatrist), by the participant's individual mental health provider, and/or a mental health emergency clinician. The participant will remain with qualified study personnel or a MIRECC clinician until the evaluation has been completed and a decision made about disposition in conjunction with the Chief of Mental Health Outpatient Clinic or the emergency mental health clinician.

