Follow-up Phase: If a participant discloses active suicidal or homicidal ideation or other clinically significant psychiatric symptomatology during the follow-up phase of the study, they will be provided with the number and encouraged to call Veterans Crisis Hotline or present to a local hospital emergency department. In the event of a seizure (or other medical issues possibly secondary to rTMS), the participant will be requested to immediately contact their primary health care provider. In the event of disclosure of the above psychiatric emergencies or a seizure, the PI or psychiatrist Co-Investigator will also be immediately notified and will contact the participant for further assessment and determine the appropriate intervention. If a participant discloses that they relapsed during the follow-up period, they will be encouraged to recontact VAPAHCs Addiction Treatment Services for re-evaluation and possible re-engagement in treatment.

Magnetic Resonance (MR) Studies

Participants will be informed of risks, using the text provided and required by Stanford University's Institutional Review Board. Our research team has been trained by MR Technologists at VAPAHCs and at Stanford to carefully pre-screen each participant for MRI safety before the MRI appointment. On-site neuroradiologists will be available for consultation. A certified MR Technologist will conduct all scans and perform a separate MR safety screen immediately prior to the scan. The scan will take place in the Diagnostic Radiology Center (DRC) at the VAPAHCs. The emergency room is nearby, in the wing next to the DRC. Minimal risks are associated with MR scanning and 3T MR scanners are now routinely used in clinical practice. Study participants who have metal implants, cardiac pacemakers, metal fragments or a known tendency for claustrophobia will not be admitted to the study. Study participants will be scanned with a metal detector before entering the 3T scanner room, and all metal objects will be removed.

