Reporting: In this study, all ADEs and AEs that occur during the acute treatment and follow-up phases will be collected and followed until resolution or the individual's participation in the study ends. All events will be recorded on the appropriate case report form. "Relatedness" involves an assessment of the degree of causality between the study intervention and the event. PIs will be asked to provide an assessment of relatedness. The assessment provided by the PI is part of the information used by the sponsor to determine if the adverse event or effect presents a participant safety concern. An ADE is deemed to be associated with the use of the study device if there is a reasonable possibility that the experience may have been caused by the device or by participation in the trial. Thus, all adverse events or effects with a reasonable causal relationship to the rTMS treatment should be considered related. A definite relationship does not need to be established. The following levels of relatedness will be used in this study:

- Not attributed to the iTBS-TMS treatment
- Possibly attributed to the iTBS-TMS treatment
- Attributed to the iTBS-TMS treatment

Serious Adverse Events (SAEs) and Unanticipated Adverse Device Effects (UADEs)

Definitions:

Serious Adverse Events (SAEs) are a subset of adverse events and are defined by the ICH for Clinical

Safety Data Management as any untoward medical occurrence that:

- Results in death
- Is life-threatening
- Requires inpatient hospitalization or prolongation of existing hospitalization
- Results in persistent or significant disability or incapacity
- Is a congenital anomaly/birth defect or
- Any other condition that, based upon medical judgment, may jeopardize the subject and require medical or surgical treatment to prevent one of the above outcomes.

An Unanticipated Adverse Device Effect (UADE) is defined as: Any serious adverse effect on health or safety or any life-threatening problem or death caused by, or associated with, a device, if that effect, problem, or death was not previously identified in nature, severity, or degree of incidence in the investigational plan or application, or any other unanticipated serious problem associated with a device that relates to the rights, safety or welfare of participants. For this study an UADE is considered a category of SAE, which will be reported on the same form.

Collection and Recording

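### The only pre-set seizure trigger, suspending enrolment after 10 participants have a seizure, is too high to work in a 40-participant trial

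*Combined protocol and SAP*

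**What the plan says.** All references are to the combined protocol and SAP.

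- **The rule.** Section 9(c), in the part on additional monitoring of seizures and suicidal ideation: "We will immediately suspend enrollment if 10 participants experience a seizure during study participation". The DMC is then asked whether enrolment should resume unchanged, resume with modifications, or end. The rule has no condition on arm, cause or relatedness, and no derivation of 10 is given.
- **Its place in the text.** It sits under a run-in heading covering screening, baseline and treatment. A separate follow-up paragraph has its own instruction ("In the event of a seizure (or other medical issues possibly secondary to rTMS"), with no count.
- **Size.** Section 2(a), Design: "participants will be randomized to active or sham iTBS-TMS conditions (20 active, 20 sham"), 40 in all.
- **Expected hazard.** Sections 2(b) and 9(a): "the estimated prevalence is very low at < 1" per cent, with no statement of whether this is per participant or per session. Both also say: "In the case of transcranial magnetic stimulation-seizures, all have occurred during stimulation".
- **Other stopping rules.** The stopping-rule item in section 9(e) refers the reader to section 2(g). That section has no safety threshold and expects the study to run until everyone has completed follow-up.

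**The concern.** Section 9(a) names seizure as the primary safety concern of the intervention. A pre-set count is there to force a pause and an outside look without waiting for anyone's judgement. That matters here because section 9(c) makes the principal investigator the stimulation operator, gives that same person the relatedness assessment, and has that person share the termination decision with the DMC. A count that cannot realistically be reached leaves the decision to pause entirely to discretion. Nine participants with seizures would oblige nothing.

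**Working it through.** **Inputs.** Trigger r = 10 (section 9(c)); n = 40 in total and 20 active (section 2(a)); stated prevalence below 1%, taken as 1% per participant (sections 2(b) and 9(a); the unit is an assumption). True risks of 5% to 30% are illustrative, because the documents give no excess-risk figure. The plan gives no operating characteristics for 10, so there is no figure of its own to reproduce.

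**Step 1: scale.** 10/40 = 25%; 10/20 = 50%. Expected participants with a seizure at 1%: 40 × 0.01 = 0.4 overall and 20 × 0.01 = 0.2 in the active arm. The trigger is 10/0.2 = 50 times the active-arm expectation.

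**Step 2: chance that the trigger fires.** Exact binomial tail, P(X ≥ 10) = Σ C(n,x) pˣ(1−p)ⁿ⁻ˣ for x = 10 to n, with independent participants all fully exposed. Because the documents say that TMS seizures occurred during stimulation, n = 20 is the natural case for device-caused events; n = 40 is the case most favourable to the rule.

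| True risk | Active arm only (n = 20) | Both arms at equal risk (n = 40) |
|---|---|---|
| 1% | 1.7 × 10⁻¹⁵ | 6.4 × 10⁻¹² |
| 5% | 1.1 × 10⁻⁸ | 2.1 × 10⁻⁵ |
| 10% | 0.0007% | 0.5% |
| 20% | 0.26% | 26.8% |
| 30% | 4.8% | 80% |

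With sham at 1% and active at 20% or 30%, the two binomials combined give 0.44% and 6.2%. An even chance of firing needs a true risk of about 48% (n = 20) or 24% (n = 40).

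These are full-sample probabilities. The rule suspends enrolment only, so a tenth seizure after accrual has closed would pause nothing.

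**Step 3: what nine would mean.** 9/40 = 22.5% (exact 95% CI 10.8% to 38.5%); 9/20 = 45% (23.1% to 68.5%).

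**Step 4: lower counts.** For r = 1, P = 1 − (1−p)ⁿ. For r = 2, P = 1 − (1−p)ⁿ − np(1−p)ⁿ⁻¹. At p = 0.01 and n = 20: 1 − 0.8179 = 18.2% for a count of 1, and 1 − 0.8179 − 0.1652 = 1.7% for a count of 2.

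| True risk (n = 20) | Count of 1 | Count of 2 | Count of 3 |
|---|---|---|---|
| 1% | 18% | 1.7% | 0.1% |
| 5% | 64% | 26% | 7.5% |
| 10% | 88% | 61% | 32% |
| 20% | 99% | 93% | 79% |

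If all 40 carry a 1% risk, a count of 1 fires 33% of the time and a count of 2 fires 6.1%.

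**The case against.** The strongest reply is that the practical gap is narrow. Section 9(c) says "The iTBS-TMS operator will monitor all participants for ear protection, coil placement, and seizure activity during all sessions", makes every seizure an SAE and withdraws the affected participant. Section 9(e) has SAEs reported within 24 hours, uses board members unaffiliated with the study, and lets any of them call an emergency meeting. The DMC can advise stopping, and the investigators can discontinue treatment if they judge the risk unacceptable. All of this stands. A reader might infer that seizures would go unseen or unreviewed until the tenth; the documents do not support that. What they lack is any provision that obliges a pause. Routine DSMB review is yearly, with about 20 participants studied per year.

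Two further readings are tempting and should not be pressed.

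- **That counting both arms is a defect.** It is not. In a double-blind trial, counting both arms lets the rule operate without unblinding.
- **That background seizures during follow-up would flood the count.** Section 1(b) does say "At least 60% of those with AUD will experience a major relapse period within 6 months of treatment", and the words of the rule reach all of study participation. But the heading above it points to screening, baseline and treatment, and follow-up has its own paragraph. The scope is ambiguous, and no background seizure rate is given. During treatment, section 9(c) also requires 7 days' abstinence and a withdrawal score of 8 or less beforehand, and withdraws anyone who drinks or uses substances.

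It is also fair to say that no particular low count follows from the documents. A count of 2 would miss a 5% active-arm risk about 74% of the time (100% − 26%). The choice belongs to the board.

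**Conclusion.** The concern holds for the size of the count. As the only numeric trial-level rule for the trial's main named hazard, 10 participants cannot act as a tripwire. At a true active-arm risk of 20%, twenty times the stated upper bound, it fires about once in 400 trials (0.26%). Even with that risk shared by both arms it fires only 26.8% of the time. The ambiguity about the window is secondary but should be settled in the same edit, since a low count is sensitive to what is counted. The reference to section 2(g) is a clerical slip and adds no weight.

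The conclusion assumes that the prevalence is per participant, that participants are independent, and that all complete exposure. The tail probabilities at 10% to 30% do not depend on the first assumption. Incomplete exposure would make 10 harder still to reach.

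**What to change.** In section 9(c):

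1. Replace 10 with a low count confirmed by the DMC/DSMB, for example 1 or 2. Keep the existing suspend-and-review wording, and keep counting both arms.
2. State the window. The simplest is any seizure, whatever its cause, from the first session to the end of the treatment phase. This avoids relying on the investigator's rating on the scale that includes "Possibly attributed to the iTBS-TMS treatment". Later seizures continue to go to the DMC/DSMB as SAEs. Motor-threshold testing precedes randomization (section 2(a)), so the board should say whether the window opens there instead.

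In section 9(e), point the stopping-rule item to section 9(c).

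**Cost.** One number, one or two sentences, one cross-reference and a short board confirmation; no extra participants or procedures. The downside is an occasional unnecessary temporary pause. At a 1% risk this is 1.7% (n = 20) to 6.1% (n = 40) for a count of 2, and 18% to 33% for a count of 1. An any-cause count would pause more often if seizures unrelated to stimulation occur during treatment, at a rate that the documents do not give.
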